8.4.2 Evaluation of tumor site phenotype

Absolute number of PD-L1/L2-bearing activated helper T cell subpopulations from biopsy at tumor site will be examined for two time points prior to conditioning and time of progression (within 18 months post-transplant) using Poisson regression analysis with GEE described in analysis of blood phenotype above.

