- To assess progression-free survival at 12 months after ASCT in patients at high risk for post-transplant recurrence including patients with persistent and recurrent high risk diffuse large B cell lymphoma, high risk and recurrent T cell lymphoma and high risk and recurrent multiple myeloma.
- To assess blood immune reconstitution, phenotype and TCR repertoire at screening (at time of informed consent), at apheresis (stem cell collection), and then serially the day 1 of week 1 of combined checkpoint inhibitors and then weeks 4, 7, 12, 18 and 26, End of Treatment, and at 9, 12, 15, and 18 months post-transplant and at time of relapse, as it occurs. Immune phenotype and TCR will be evaluated as follows:

T cell repertoire analysis

TCR Immunoseg for Vbeta CDR3 highest frequency specificities.

Real-Time PCR analysis:

T-bet(Th1); STAT3, RORgamma t (TH17); STAT6 (Th2); FoxP3 (Treg), granzyme A (GZMA) and perforin (PRF1)

Flow Cytometric Phenotype Analysis for:

T Cells:

CD3; CD4; CD8; CD4+CD25+PD1+; CTLA-4
Follicular Helper T: CD3+,CD4+,CXCR5+,PD1+
CD4 and CD8 T naïve (RO-; CCR7+)
Central Memory: (T^{CM};RO+,CCR7+)
Effector Memory (T^{EM}, RO+,CCR7-)
Terminally differentiated effector memory (T^{EMRA}; RO-, CCR7-)
T regulatory cells (Treg): CD4+,CD25^{hi}, CD127^{low}, CD39+, CD152^{hi}, RO- (resting); CD4+,CD25^{hi}, CD127^{low}, CD39+, CD152^{hi}, RO+ (activated)

Dendritic Cells:

Lin-, CD11c+, CD1a+, CD80 $(B7-1)^{low}$, CD86 $(B7-2)^{low}$, MHC Class II^{low} (DC resting); CD11c+, CD1a+, CD123-, CD80^{hi}, CD86^{hi}, HLADR^{hi} (DC1 activated); HLADR^{hi}, CD11c-, CD123+, PDL-1+ (DC2)

Macrophages:

HLADR+, CD14+, CD64+, CD25+, CCR7+ (M1); HLADR+, CD14+, CD64-, CD206+, CD25-, CCR7-, CD209+, PDL-1+ (M2)

Myeloid derived suppressor cells:

HLADR-/low, CD11b+, CD14+,CD33+hi,CD34+, CD66b-, PDL-1+ (M-MDSC); HLADR-, CD11b+, CD14-,CD33+low,CD34+, CD66b+, PDL-1+ (G-MDSC)

B Cells:

CD19+, B7-1^{low}, B7-2^{low}, MHC Class II^{low} (resting); CD19+, B7-1^{hi}, B7-2^{hi}, MHC Class II^{hi} (activated)

NK cells:

CD16+, CD3-, CD56+

NKT Cells:

CD16+, CD3+, CD56+

Plasma Cytokine levels: Multiplex 25 Cytokine - Luminex

GM-CSF, IL-1b, IL-1RA, IL-2, IL-2R, IL-4, IL-5, IL-6, IL-7, IL-8, IL-10, IL-12, IL-13, IL-15, IL-17, TNF alpha; MCP-1, MIP1a, MIP1b, MIG, RANTES, IFN-alpha, IFN-gamma, IP-10, Eotaxin

- To determine the toxicities resulting from administration of the treatments.

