- To assess tumor site immune phenotype, T cell repertoire and PD L1/2 expression when tissue available for biopsy prior to autologous transplant conditioning and

then at time of progression (within 18 months) after autologous transplant conditioning.

The tertiary objectives are:

• To identify specific intestinal microbial strains associated with improved outcome in autologous stem cell transplantation patients treated with combined checkpoint inhibitors. The overall microbial composition in stool samples of patients will be analyzed at screening, preconditioning (to be collected within 48 hours prior to transplant admission), at engraftment (within 72 hours of ANC ≥ 500), and then serially, on day 1 of week 1 (to be collected within 48 hours prior to clinic visit) and then weeks 4, 7, 12, 18, and 26, End of Treatment and 9, 12, 15 and 18 months post-transplant, and at time of relapse, as it occurs. A 16S ribosomal RNA (rRNA) miSeq Illumina platform will be used for overall microbial composition and quantitative real-time PCR analysis will validate the specific microbial strains identified by miSeq.

Phase IIA

The primary objectives of this study are:

• To assess progression-free survival at 18 months after ASCT in patients in cohorts that were deemed safe in Phase Ib (no more than 3 treatment-related toxicity) and at least 4 of 7 patients progression free at 18 months in the Phase Ib.

The secondary objectives of this study are:

- To assess complete response rate at 3, 6 and 12 months after ASCT in patients at high risk for post-transplant recurrence including patients in the successor expansion cohorts following the Phase Ib trial.
- To assess progression-free survival at 12 months after ASCT in patients at high risk for post-transplant recurrence including patients with in the successor expansion cohorts following the Phase Ib trial.
- Determine the toxicities resulting from administration of the treatments in patients enrolled in the successor expansion cohorts following the Phase Ib trial.
- To assess blood immune reconstitution, phenotype and TCR repertoire at screening (at time of informed consent), at apheresis (stem cell collection), and then serially the day 1 of week 1 of combined checkpoint inhibitors and then weeks 4, 7, 12, 18 and 26, End of Treatment, and at 9, 12, 15, and 18 months post-transplant and at time of relapse, as it occurs.

The tertiary objectives are:

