- For all groups: Acquisition of tumor tissue biopsy (either new or archival tissue, if available) or bone marrow biopsy (if known involvement) for evaluation of PD1/PDL1 expression and baseline tumor immune profile. Tumor Biopsies and/or Bone Marrow Biopsies for Lymphoma subjects (Groups A through D) and Bone Marrow Biopsies for Multiple Myeloma subjects (Groups E & F) will be collected at screening, end of treatment, complete response, and at relapse, if clinically indicated. For Bone Marrow Biopsies, the research sample will be collected (aspirate, send the first pull, yellow top tube) to [name] lab. Additional samples for all disease groups will be sent to pathology for immunostaining of fixed tissue for PDL1 expression on tumor cells and for the in situ presence of CD4 and CD8 T cells with PD1 expression. If viable biopsy material is unavailable for research purposes, [name] lab will access fixed archival tumor materials for preparing tumor lysates and possibly for retrieving T cell DNA for repertoire analysis. Samples for Georgetown University subjects are to be shipped via Fed Ex on the day of collection tubes banded in sealed plastic bag and wrapped in bubble wrap at room temperature to [name] lab.

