- To assess progression-free survival at 12 months after ASCT in patients at high risk for post-transplant recurrence including patients with persistent and recurrent high risk diffuse large B cell lymphoma, high risk and recurrent T cell lymphoma and high risk and recurrent multiple myeloma.
- To assess blood immune reconstitution, phenotype and TCR repertoire at screening (at time of informed consent), at apheresis (stem cell collection), and then serially the day 1 of week 1 of combined checkpoint inhibitors and then weeks 4, 7, 12, 18 and 26, and at 9, 12, 15, and 18 months post-transplant and at time of relapse, as it occurs. Immune phenotype and TCR will be evaluated as follows:

T cell repertoire analysis

TCR Immunoseg for Vbeta CDR3 highest frequency specificities.

Real-Time PCR analysis:

T-bet(Th1); STAT3, RORgamma t (TH17); STAT6 (Th2); FoxP3 (Treg), granzyme A (GZMA) and perforin (PRF1)

Flow Cytometric Phenotype Analysis for:

T Cells:

CD3; CD4; CD8; CD4+CD25+PD1+; CTLA-4 Follicular Helper T: CD3+,CD4+,CXCR5+,PD1+ CD4 and CD8 T naïve (RO-; CCR7+) Central Memory: (TCM;RO+,CCR7+) Effector Memory (TEM, RO+,CCR7-)

Terminally differentiated effector memory (TEMRA; RO-, CCR7-)

T regulatory cells (Treg): CD4+,CD25hi, CD127low, CD39+, CD152hi, RO-(resting); CD4+,CD25hi, CD127low, CD39+, CD152hi, RO+ (activated)

Dendritic Cells:

Lin-, CD11c+, CD1a+, CD80 (B7-1)low, CD86 (B7-2)low, MHC Class Illow (DC resting); CD11c+, CD1a+, CD123-, CD80hi, CD86hi, HLADRhi (DC1 activated); HLADRhi, CD11c-, CD123+, PDL-1+ (DC2)

Macrophages:

HLADR+, CD14+, CD64+, CD25+, CCR7+ (M1); HLADR+, CD14+, CD64-, CD206+, CD25-, CCR7-, CD209+, PDL-1+ (M2)

Myeloid derived suppressor cells:

HLADR-/low, CD11b+, CD14+,CD33+hi,CD34+, CD66b-, PDL-1+ (M-MDSC); HLADR-, CD11b+, CD14-,CD33+low,CD34+, CD66b+, PDL-1+ (G-MDSC)

B Cells:

CD19+, B7-1low, B7-2low, MHC Class Illow (resting); CD19+, B7-1hi, B7-2hi, MHC Class Ilhi (activated)

Amendment9 09NOV2021 Page 35 of 77

NK cells:

CD16+, CD3-, CD56+

NKT Cells:

CD16+, CD3+, CD56+

Plasma Cytokine levels: Multiplex 25 Cytokine - Luminex

GM-CSF, IL-1b, IL-1RA, IL-2, IL-2R, IL-4, IL-5, IL-6, IL-7, IL-8, IL-10, IL-12, IL-13, IL-15, IL-17, TNF alpha; MCP-1, MIP1a, MIP1b, MIG, RANTES, IFN-alpha, IFN-gamma, IP-10, Eotaxin

- To determine the toxicities resulting from administration of the treatments.

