- To assess tumor site immune phenotype, T cell repertoire and PD L1/2 expression when tissue available for biopsy prior to autologous transplant conditioning and then at time of progression (within 18 months) after autologous transplant conditioning.

The tertiary objectives are:

• To identify specific intestinal microbial strains associated with improved outcome in autologous stem cell transplantation patients treated with combined checkpoint inhibitors. The overall microbial composition in stool samples of patients will be analyzed at screening, preconditioning (to be collected within 48 hours prior to transplant admission), at engraftment (within 72 hours of ANC ≥ 500), and then serially, on day 1 of week 1 (to be collected within 48 hours prior to clinic visit) and then weeks 4, 7, 12, 18, and 26, End of Treatment, and 9, 12, 15 and 18 months post-transplant, and at time of relapse, as it occurs. A 16S ribosomal RNA (rRNA) miSeq Illumina platform will be used for overall microbial composition and quantitative real-time PCR analysis will validate the specific microbial strains identified by miSeq.

Phase IIA

Primary Objective

• To assess progression-free survival at 18 months after ASCT in patients in cohorts that were deemed safe in Phase Ib (no more than 3 treatment-related toxicity) and at least 4 of 7 patients progression free at 18 months in the Phase Ib.

Secondary Objectives

- To assess complete response rate at 3, 6 and 12 months after ASCT in patients at high risk for post-transplant recurrence including patients in the successor expansion cohorts following the Phase Ib trial.
- To assess progression-free survival at 12 months after ASCT in patients at high risk for post-transplant recurrence including patients with in the successor expansion cohorts following the Phase Ib trial.
- Determine the toxicities resulting from administration of the treatments in patients enrolled in the successor expansion cohorts following the Phase Ib trial.
- To assess blood immune reconstitution, phenotype and TCR repertoire at screening (at time of informed consent), at apheresis (stem cell collection), and then serially the day 1 of week 1 of combined checkpoint inhibitors and then weeks 4, 7, 12, 18 and 26, and at 9, 12, 15, and 18 months post-transplant and at time of relapse, as it occurs.

Tertiary Objectives

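### The only tumour-site analysis (8.4.2) counts PD-L1/L2-bearing helper T cells, which no listed assay measures, while the tissue stains that are listed have no named analysis and the count has no denominator

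*Combined protocol and SAP*

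**What the plan says.** The Phase Ib secondary objective in 1.0, repeated in the synopsis and in 8.0, is "To assess tumor site immune phenotype, T cell repertoire and PD L1/2 expression when tissue available for biopsy prior to autologous transplant conditioning", and again at progression within 18 months. The closing paragraph of 2.1 names PD-L1 and PD-L2 separately.

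The analysis in 8.4.2 reads: "Absolute number of PD-L1/L2-bearing activated helper T cell subpopulations from biopsy at tumor site will be examined for two time points". It takes its method from the blood analysis in 8.3.4, which is Poisson regression by GEE with a log link and an independence covariance structure.

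On tissue, 6.1 collects new or archival tumour, or marrow where involvement is known, "for evaluation of PD1/PDL1 expression and baseline tumor immune profile". The stains it itemises, repeated in Appendix D footnote k, are "immunostaining of fixed tissue for PDL1 expression on tumor cells and for the in situ presence of CD4 and CD8 T cells with PD1 expression". Section 6.2.3 adds a confirmatory node and/or marrow biopsy at relapse, partly for immunophenotyping, and lists no markers.

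The flow list in 1.0 and 8.0 stands under the blood immune reconstitution objective. Its first T-cell line is "CD3; CD4; CD8; CD4+CD25+PD1+; CTLA-4".

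**The concern.** An analysis section should name a variable that the trial's own assays produce. Here the named variable is a T cell carrying the ligand (PD-L1 or PD-L2). The itemised tissue stains look for the receptor (PD-1) on T cells and for PD-L1 on tumour cells. The cell type in 8.4.2 appears elsewhere only in 2.3, as a finding of an earlier pidilizumab trial.

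Three things follow if the text stays as it is:

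- The prespecified analysis may have no data.
- The stains that are listed will be summarised in a way chosen after they have been seen.
- The PD-L2 element will have no stated source.

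Separately, an absolute number from a biopsy has no fixed denominator. A change between the two time points could reflect sample size rather than biology.

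**Working it through.** No sample size, power or alpha is attached to this analysis, so there is no plan figure to reproduce. The check sets the variable against each itemised assay.

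| Source | PD-L1 on T cells | PD-L2 on any cell | What it does give |
|---|---|---|---|
| Tissue stains (6.1; Appendix D footnote k) | no | no | PD-L1 on tumour cells; PD-1 on CD4 and CD8 cells; no activation marker |
| Flow list (1.0, 8.0; given for blood) | no | no | PD-1 on CD4+CD25+ cells; PD-L1 on DC2, M2 and both myeloid suppressor subsets |
| PCR list (1.0, 8.0) | no | no | transcription factors, granzyme A, perforin |
| Blood models (8.3.4) | no | no | activated T cells split by PD-1 status |

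In the flow list PD-L1 is attached to non-T populations, for example "CD11c-, CD123+, PDL-1+ (DC2" and "CD25-, CCR7-, CD209+, PDL-1+ (M2".

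**The reverse check: which section 8 analysis uses the listed tissue stains?**

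- 8.3.4 limits its longitudinal analyses to blood samples.
- 8.4.2 names neither PD-L1 on tumour cells nor PD-1-positive CD4 or CD8 cells.
- 8.4.3 gives generic summary rules after demographics, with no tumour endpoint, pairing or time-point comparison.

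So no analysis is named for them.

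**The denominator.** Expected count = cell density × amount of evaluable tissue. At equal density, the rate ratio between two samples equals the ratio of their tissue amounts. The documents give no tissue amounts. As an assumption, a ratio from 0.5 to 2 gives an apparent rate ratio from 0.5 to 2.0 with no biological change. Blood draws are standardised (68 mL in Appendix J). Tissue may be new or archival, nodal or marrow, and of any size. Neither 8.3.4 nor 8.4.2 states an offset.

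**How many pairs to expect.** Section 8.1 gives 7 patients per cohort and a historical 18-month PFS of 40–50%.

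- Patients who progress or die, per cohort: 7 × (1 − 0.50) = 3.5 to 7 × (1 − 0.40) = 4.2.
- At the expansion threshold of 4 of 7 progression-free: 7 − 4 = 3.
- Four lymphoma cohorts together (28 patients): 28 × 0.50 = 14 to 28 × 0.60 = 16.8 at the historical rates, or 4 × 3 = 12 at the threshold.

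These are upper limits on pairs. Deaths without progression give no second sample, and tissue depends on availability and clinical indication. Groups E and F are discontinued and their final numbers are not given, so they are left out.

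**The case against.** The strongest reply is that silence is not proof.

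- Section 6.1 collects tissue for a tumour immune profile without itemising it, sends a research aspirate to a laboratory, and introduces the pathology stains as additional samples. Section 6.2.3 also leaves its tumour immunophenotyping un-itemised.
- The flow list is for blood and is not said to be the complete tissue panel.
- Activated helper T cells are within that list, since CD4+CD25+ appears there. Only the ligand is missing.
- The objective is secondary, Phase Ib only, and conditional on tissue.

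Most of this stands, and it limits the conclusion. A reader might infer that the objective cannot be answered at all. The documents do not support that: the objective does not confine PD-L1/2 to T cells, and the listed stains bear directly on its PD-L1 and phenotype parts. A reader might also infer that the input to 8.4.2 does not exist, or that PD-L2 can never be reported. That is unproven, because an unlisted assay could supply either one.

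The reply does not remove the mismatch. The one analysis variable differs from the stains that are stated, and the stated stains have no analysis. If a research panel does measure PD-L1 or PD-L2 on tissue T cells, it has to be named. On the offset, 8.4.2 may intend some standardisation, but it states none and calls the quantity an absolute number. The ratio of 2.0 illustrates the mechanism; it is not an estimate for this trial.

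**Conclusion.** The point holds in a limited form. No listed assay provides the 8.4.2 variable or the PD-L2 element of the objective. The listed readouts, PD-L1 on tumour cells and PD-1-positive CD4 and CD8 cells, have no named analysis. The count model states no denominator for tissue of differing size.

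This rests on the itemised assays in 1.0, 6.1, 8.0 and Appendix D. It would be partly answered if the un-itemised tissue panel were shown to include PD-L1 and PD-L2 on activated helper T cells. The missing analysis of the listed stains and the missing denominator would remain.

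The reach is one Phase Ib, tissue-dependent secondary objective. The primary endpoints, sample size, stopping rules and expansion decision are untouched. The correction is worth making before any tissue data are analysed, because it is cheap and prevents tumour endpoints from being chosen after the fact.

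**What to change.** Rewrite 8.4.2 around the stains already listed:

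1. Percent of tumour cells positive for PD-L1.
2. PD-1-positive CD4 cells and PD-1-positive CD8 cells, each relative to evaluable area or to total nucleated or T cells. Use a cell-based denominator for marrow, where area does not apply. If a count model is kept, enter the log of that denominator as an offset.
3. Report both descriptively, as within-patient change from pre-conditioning to progression in patients with both samples. Pool across cohorts and list by cohort, since few pairs are expected with 7 patients per cohort.

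Keep the PD-L1/L2 T-cell variable and the PD-L2 part of the objective only if the assay that yields them is named. Otherwise remove them from 1.0, 8.0 and 8.4.2, and from the matching text in the synopsis and 2.1. Tumour T cell repertoire belongs to the same objective and also has no named tumour-site analysis. This rewrite does not cover it, so one sentence should say how it will be reported.

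Cost: a wording amendment, and a denominator recorded by pathology on slides already being read. No new biopsy is needed. The downside is that the PD-L2 claim may be dropped.

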In humans, PD-L1 is constitutively expressed on both hematopoietic cells such as macrophages and T cells as well as non-hematopoietic cells such as lung, vascular endothelial cells, and placental syncitiotrophoblasts. Aberrant expression of PD-L1 in tumor cells has been shown to enhance apoptosis of activated tumor-specific T cells *in vitro*. Additionally, the expression of PD-L1 may protect tumor cells from T cell-induced apoptosis. Retrospective analyses of several human tumor types suggest that over-expression of PD-L1 facilitates tumor evasion of immune surveillance²⁴. In renal cell carcinoma, high surface expression levels of PD-L1 are correlated with tumor aggressiveness. Subjects with high tumor and/or lymphocyte PD-L1 levels are 4.5 times more likely to die from their cancer than subjects exhibiting low levels of PD-L1 expression²⁵. In multivariate analysis, high expression of PD-L1 in melanoma is an independent predictor of vertical growth of primary melanomas and of worse outcome²⁶.

Nivolumab is a fully human, IgG4 (kappa) isotype, mAb that binds to PD-1. Blockade of the PD-1 pathway by nivolumab resulted in a reproducible enhancement of T cell proliferation in a mixed lymphocyte reaction (MLR) assay. The effect of nivolumab on an antigen-specific recall response was investigated using a CMV-restimulation assay with human peripheral blood mononuclear cells (PBMCs), and was evaluated by ELISA. These data indicated that nivolumab, versus an isotype-matched control antibody, augmented IFN-γ secretion from CMV-specific memory T cells in a dose dependent manner²⁷.

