6.2 Evaluation and Response

6.2.1 For Groups A, B, C, and D:

- PET-CT scan and/or CT scan with intravenous/oral contrast of neck, chest, abdomen and pelvis will be performed for response evaluation 90-100 days post ASCT, 180-200days post ASCT, 360-380 days post ASCT and 540-560 days post ASCT. Response criteria will follow the Lugano Classification (see Appendix B). Both PET/CT and CT scan should be done within 30 days prior to initiation of ASCT conditioning for baseline response evaluation purposes. Either PET/CT or CT scan are acceptable for response evaluation after ASCT, and should be compared to the pre-ASCT baseline scan.
- Physical exam, laboratory work-up and correlative studies will be performed as delineated in the Clinical Trial Flowchart (Appendix D)

Amendment9 09NOV2021 Page 32 of 77

6.2.2 For Groups E and F:

- Serum protein electrophoresis with immunofixation, quantitative serum IgG, IgM, IgA (IgE or IgD in cases where this is the involved immunoglobulin), serum free light chains, 24-hour urine for protein electrophoresis with immunofixation and protein quantification will be collected for response evaluation 30-40 days post ASCT, 60-70 days post ASCT, 90-100 days post ASCT, 180-200 days post ASCT, 270-290 days post ASCT, 360-380 days post ASCT, 450-470 days post ASCT and 540-560 days post ASCT. Response criteria will follow the International Myeloma Working Group (IMWG) Uniform Response Criteria for Multiple Myeloma (see Appendix C). For patients who achieve CR by IMWG Criteria, a bone marrow biopsy will be required for confirmation and tumor immunophenotype analysis
- Physical exam, laboratory work-up, and correlative studies will be performed as delineated in the Clinical Trial Flowchart (Appendix D)

6.2.3 For All Groups:

- If a patient signs consent but does not receive treatment, the patient will not be evaluable and no further safety information will be collected. The slot will be released and may be re-assigned to another patient.
- If there is progressive disease or relapse documented by any of the criteria, a confirmatory lymph node and/or bone marrow biopsy will be performed for confirmation of disease relapse and tumor immunophenotype studies.

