8.1 Determination of Sample Size

- The Phase Ib feasibility trial will require 42 patients divided in 6 cohorts, with 7 patients each. Enrolled patients will have hematologic malignancies with a high risk for post-autologous stem cell transplant recurrence including patients with persistent and recurrent high risk diffuse large B cell lymphoma, high risk and recurrent T cell lymphoma and high risk and recurrent multiple myeloma.
- The Phase IIA will require up to 148 patients, assuming all cohorts followed in Phase Ib meet the criteria for expansion.

Accrual goal is 7 patients per cohort. Accrual period goal is 36 months. Patients will accrue to study by disease groups (cohorts) and followed separately by group for incidence and severity of toxicity, ability to receive intended schedule of combined checkpoint inhibitors and for complete response and progression free survival (PFS) rates. Complete response and progression free survival rates will be compared to published standards for each disease group. Expected PFS at 18 months (PFS18) for all post-transplant groups without checkpoint inhibitors is 40-50%¹⁻³. Groups A, B, C, and D with PFS at 18 months in 4 or more patients (57%) will be considered for eligibility in a successor phase IIa expansion trial. The primary efficacy endpoint of the phase Ib portionis to achieve PFS of 18 months in ≥4 patients per cohort (≥57%).

Phase Ib

The initial part of the trial titled is designed as a feasibility Phase Ib study. This will determine which of 6 cohorts of patients would be studied in an expansion Phase IIa trial. In this pilot feasibility study, designed to assess the safety of the combined checkpoint inhibitor, sample size was not performed to estimate power, as it was designed to obtain initial estimates of toxicity to inform the successor trial Phase IIA. Therefore, this pilot feasibility study is not powered to detect significant differences in PFS. We have preemptively established a cut-off of ≥57% PFS at 18 months as the minimum benefit needed to proceed to Phase IIa for each individual cohort, if a maximum of 3 patients in each cohort experience severe adverse events which would lead to trial discontinuation (for that particular cohort). Historical data for such patient populations predicts PFS 40-50% at 18 months.

Phase IIa

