- 2. Within each subset, the following separate longitudinal analysis of cell counts over time will conducted:
 - i. Count of dendritic cells as a function of time (14 timepoints) and status (DC1 versus DC2).
 - ii. Count of DC2 as a function of time (14 timepoints) and PDL-1+/- status,
 - iii. Count of macrophages as a function of time (14 timepoints) and status (M1 versus M2)
 - iv. Count of M2 cell as a function of time (14 timepoints) and PDL-1+/- status,
 - v. Count of CD4 T cells as a function of time (14 timepoints) and follicular helper function status.
 - vi. Count of T cells as a function of time (14 timepoints) and activated status (activated versus naïve),
- vii. Count of activated T cells as a function of time (14 timepoints) and PD1+/- status,
- viii. Count of Tregs as a function of time (14 timepoints) and activated status (activated versus resting),
- ix. Count of memory T cells as a function of time (over 14 timepoints) and type of memory cells (effector versus central memory versus terminally differentiated effector memory,
- x. Count of B cells as a function of time (14 timepoints) and activated status (activated versus resting),
- xi. Count of myeloid suppressor cells as a function of time (14 timepoints) and PDL-1+/-status,

For these count variables, Poisson Regression Analysis based on generalized estimating equations (GEE) method will be performed by utilizing the procedure PROC GENMOD SAS 9.4 with Poisson distribution, log link function and independent covariance structure.

Continuous variables such as cytokine levels (GM-CSF, IL-1b, IL-1RA, IL-2, IL-2R, IL-4, IL-5, IL-6, IL-7, IL-8, IL-10, IL-12, IL-13, IL-15, IL-17, TNF alpha; MCP-1, MIP1a, MIP1b, MIG, RANTES, IFN-alpha, IFN-gamma, IP-10, Eotaxin) will be examined over time (14 timepoints) using mixed model repeated measures (MMRM) by utilizing PROC MIXED SAS 9.4. In both of the models to be fit to these immune markers, the status of infection as a time-dependent covariate will be included to examine the effect of both time and infection on cell cytokine levels.

8.3.5 Longitudinal analysis of the gut microbiome.

The time points of stool sample collection are:

- 1) Screening Visit (up to 7 days post consent). If patient signs consent within 7 days of transplant admission, stool sample collection will start from item "2" (Preconditioning)
- 2) Preconditioning (to be collected within 48 hours prior to transplant admission)
- 3) Engraftment, (within 72 hours of ANC > 500)

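### Section 8.4.2 does not limit the tumour-site comparison to patients with both biopsies, so a baseline difference between later progressors and non-progressors would be reported as a change at progression

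*Combined protocol and SAP*

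**What the plan says.** The Phase Ib secondary objectives (section 1.0, repeated in 8.0) include tumour-site immune phenotype, T cell repertoire and PD-L1/L2 expression, "when tissue available for biopsy prior to autologous transplant conditioning and" then at progression within 18 months. Phase IIA has no such objective.

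Section 8.4.2 gives the analysis: numbers of PD-L1/L2-bearing activated helper T cells "will be examined for two time points prior to conditioning and time of progression (within 18 months post-transplant) using Poisson regression analysis with GEE", as already set out for the blood phenotype. Section 8.3.4 specifies that model: "PROC GENMOD SAS 9.4 with Poisson distribution, log link function and independent covariance structure".

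Two passages settle who can supply tissue.
- Screening (section 6.1): "For all groups: Acquisition of tumor tissue biopsy (either new or archival tissue, if available) or bone marrow biopsy (if known involvement").
- Progression (section 6.2.3): "If there is progressive disease or relapse documented by any of the criteria, a confirmatory lymph node and/or bone marrow biopsy will be performed".

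No text limits 8.4.2 to patients with both samples, adds a term for later progression, or names an analysis set. Section 8.2 assigns intent-to-treat to response and PFS, and as-treated to safety.

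**The concern.** The two time points are sampled from different sets of patients. Before conditioning, tissue can come from anyone. At progression, it can come only from patients whose treatment failed. The missing second sample is therefore not incidental dropout: in a patient who does not progress, it does not exist. A within-patient change from baseline to progression is defined only in progressors.

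The named model does not link a patient's two records when it estimates the time effect. It compares one group's average at relapse with a broader group's average at baseline. If the two kinds of patient start with different counts, the result mixes that starting difference with any real change. An apparent gain or loss of these cells at relapse could then be taken as biology when no tumour changed.

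**Working it through.** **The plan's own figure.** Section 8.4.2 states no effect size, sample size or power, so there is none to reproduce.

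**Step 1: what the model estimates.** With a log link, a time indicator and an independence structure, the fitted mean at each time point is the raw mean of the records at that time. So

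exp(time effect) = mean of all progression samples / mean of all baseline samples.

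The time-dependent infection covariate in section 8.3.4 does not separate later progressors from the rest, so it does not remove the problem.

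**Step 2: expected ratio with no true change.** Let M be the mean baseline count in non-progressors, rM that in later progressors, and p the share of later progressors among patients with baseline tissue.
- Baseline mean: p·rM + (1−p)·M
- Progression mean with no change: rM
- Ratio: r / (p·r + 1 − p)

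This assumes that tissue availability does not depend on the counts.

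**Step 3: inputs.**
- p is taken as 1 − PFS18. Section 8.1 gives "Historical data for such patient populations predicts PFS 40-50% at 18 months" and an expansion target of 57%, so p = 0.60, 0.50 and 0.43. Deaths without progression make p smaller, which moves the ratio closer to r and so further from 1.
- r is not in the documents. A range is assumed.

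**Step 4: results.** Example at p=0.43, r=0.5: 0.5 / (0.43×0.5 + 0.57) = 0.5 / 0.785 = 0.64.

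| r | PFS18 57% (p=0.43) | PFS18 50% (p=0.50) | PFS18 40% (p=0.60) |
|---|---|---|---|
| 0.5 | 0.64 | 0.67 | 0.71 |
| 0.67 | 0.78 | 0.80 | 0.84 |
| 1 | 1.00 | 1.00 | 1.00 |
| 1.5 | 1.23 | 1.20 | 1.15 |

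**Step 5: simulated rejection rates with no true change.** The settings are 28 patients (four lymphoma cohorts of 7), PFS18 57%, Poisson counts with log-scale patient SD 0.7 and occasion SD 0.4, and a nominal two-sided 5% test with robust variance. Every patient has baseline tissue and every progressor has a second sample. The SDs and the complete tissue are assumptions.

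| r | Analysis as written, rejection | Paired ratio in progressors |
|---|---|---|
| 0.5 | 47% | about 1.00 |
| 0.67 | 25% | about 1.00 |
| 1 | 10% | about 1.00 |
| 1.5 | 20% | about 1.00 |

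The 10% at r=1 is the small-sample excess of the robust test. The rise above it comes from selection.

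**Step 6: how the paired test behaves.** Pairs are few: 28×0.43 = 12.0 at best, or 7×0.43 = 3.0 per cohort. With the uncorrected robust variance the paired test also rejects too often, 13–14% with complete tissue. If each sample is available half the time (assumed), the expected number of pairs is 28×0.43×0.5×0.5 = 3.0. About 40% of simulated trials then have fewer than three pairs, and in the rest the robust test rejects about 29%. A paired t-test on log ratios holds about 5%.

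**The case against.** **The plan does not say that unpaired baselines are kept.** True: 8.4.2 names no analysis set, and the objective depends on tissue being available. But nothing excludes unpaired records, and the named model uses every record it is given.

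**The objective may be descriptive.** The wording is to assess the phenotype at each time, and separate means would describe that fairly. This stands for description. It does not cover a two-time-point regression whose time effect will be read as change.

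**The bias is conditional.** This stands. A reader might infer that the plan is bound to report a false change, or that it will show a loss of cells at relapse. The documents support neither. At r=1 there is no bias. The nearest support, in section 2.2, is that "high expression of PD-L1 in melanoma is an independent predictor of vertical growth of primary melanomas and of worse outcome", with a similar statement for renal cancer. Those are other tumours and not this T cell subset. If anything they point to r above 1, where the ratio would be inflated. They show only that equal baselines cannot be presumed.

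**Larger trials would make it worse.** A reader might apply the problem to the Phase IIA sizes of 37 per cohort or 148 in total. The objective is listed for Phase Ib only, so error rates at those sizes do not describe this analysis.

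**Pairing is not always more precise.** This stands. In the simulation above the paired estimate was the more precise. With the two SDs exchanged, as could happen when archival tissue is compared with a fresh biopsy, the SD of the paired log ratio is 0.35 against 0.30–0.32 for the analysis as written.

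**Conclusion.** The concern holds in a conditional form. As written, section 8.4.2 compares progressors at relapse with everyone who has baseline tissue, which is not a within-patient change. At PFS18 57% and no true change, a baseline ratio between 0.5 and 1.5 would be reported as a ratio between 0.64 and about 1.23, and at PFS18 40% as 0.71 to 1.15. The size and direction in this trial cannot be known, because r is not in the documents. The figures rest on tissue availability being unrelated to the counts. The rejection rates also rest on the assumed SDs and complete tissue.

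The consequence is limited. This is an exploratory Phase Ib secondary analysis with no stated hypothesis or power, and expansion depends on toxicity and PFS18. A reader might infer that the trial plans to claim a mechanism of escape from treatment. The documents plan no such claim; the risk lies in how a reported time effect would be read. It is worth correcting because the contrast itself is wrong and correcting it costs little.

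**What to change.** In section 8.4.2:
- Estimate change only in patients with both a pre-conditioning and a progression biopsy, as a within-patient log ratio.
- Use a small-sample method, a paired t-test or an exact signed-rank test, and not the uncorrected robust-variance test.
- Report the number of pairs, and give only descriptive results when pairs are very few.
- Summarise unpaired biopsies descriptively.
- Compare baseline counts of later progressors and non-progressors as a separate analysis.

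The cost is SAP wording and a few lines of code, with no new biopsies. Unpaired biopsies, including progression samples without a baseline, leave the change estimate. Precision may be slightly lower if within-patient variation exceeds between-patient variation.
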